Study Protocol

Study Title: Portal Vein Flow Variability to Quantify Right-Sided Hemodynamic Congestion: A Proof-Of-Concept study

Study Acronym: PORTAL

Phase of Development: N/A

Protocol Number: 3

Protocol Version and Date: Version 3.0, May 30th, 2022

EudraCT Registry Number: N/A

ClinicTrials.gov Registry Number:

Investigational product: None

Sponsor: UZ Brussel

Coordinating/Principal Investigator: [name]. [name]

The information contained in this document is the property of the Sponsor/Coordinating Investigator and may not be reproduced, published or disclosed to others without written authorization of the Sponsor/Coordinating Investigator.

PROTOCOL SIGNATURE PAGE

Protocol Version and date: Version 3.0, May 30th, 2022

Protocol Title: Portal Vein Flow Variability to Quantify Right-Sided Hemodynamic Congestion: A Proof-Of-Concept study

Sponsor: UZ Brussel

Principal Investigator: [name]. [name]

[figure not shown]
I agree:

- to assume responsibility for the proper conduct of this study
- to conduct the study in compliance with this protocol and any future amendments
- not to implement any deviations from or changes to the protocol without prior review and written approval from the Ethics Committee, except where necessary to eliminate an immediate hazard to the subjects, or for administrative aspects of the study (where permitted by all applicable regulatory requirements)
- that I am thoroughly familiar with the appropriate use of the investigational drug, as described in this protocol
- to ensure that all persons assisting me with the study are adequately informed about the investigational drug and their study-related duties and functions as described in the protocol
- that I am aware of and will comply with the current good clinical practice (GCP) guidelines and ethical principles outlined in the Declaration of Helsinki
- to conduct the study in accordance with all applicable laws and regulations

Printed name: [name]

Signature

Date: 30/05/2022

Study Protocol

Portal Vein Flow Variability to Quantify Right-Sided Hemodynamic Congestion (PORTAL):

A Proof-Of-Concept study

[name] M.D. Pharm.D. & [name] M.D. Ph.D.

1. Study design

- Prospective
- Interventional
- Single centre (UZ Brussel)
- Proof-of-concept

2. Purpose & rationale

Right ventricular hemodynamic congestion or elevated central venous pressure (CVP) is an independent predictor of morbidity and mortality in heart failure (1). Persistent elevations of right atrial pressure (RAP) cause upstream venous congestion in the abdominal compartment, which leads to organ dysfunction in liver and kidney function, with effects on the lungs as well (2), (3). According to contemporary echocardiography guidelines, non-invasive assessment of RAP is performed by measuring inferior vena cava (IVC) size and respiratory variation (i.e., collapsibility) (4). However, assumptions that are not always valid (especially in critically ill patients) hamper the use of this technique and misinterpretation due to 'pseudo-collapse' could lead to erroneous interpretation.

Portal vein Doppler flow patterns may be a simple and attractive tool to aid in the evaluation of RAP/CVP and predicts acute kidney injury after cardiac surgery (5). The aim of this proof-of-concept study is to assess the feasibility of portal vein Doppler flow to quantify RAP/CVP in a population of consecutive patients with advanced heart failure undergoing invasive right heart catheterization.

3. Objective

To evaluate the accuracy of the portal vein pulsatility index (PVPI=Vmax-Vmin)/Vmax) to quantify invasively measured right-sided venous pressures.

4. Study population

a. Inclusion criteria

- At least 18 y/o and able to provide informed consent
- Consecutive patients scheduled for right heart catheterisation by a dedicated heart failure specialist at the Centre of Cardiovascular Diseases (University Hospital Brussels, Jette, Belgium)

b. Exclusion criteria

- Major anatomical variations of the portal veins (agenesis of left and right portal vein) and/or arterio-portal vein fistula
- Patients with Child-Pugh B or C liver cirrhosis or liver transplant
- Body Mass Index < 20 kg/m²

5. Intervention

All patients will undergo right heart catheterisation for clinical reasons. As part of the hemodynamic assessment, RAP and CVP assessed at the level of the intrathoracic and intra-abdominal IVC as well as the vena Hepatica is measured. In addition, the hepatic venous wedge pressure (HVWP) is measured.

PVPI is simultaneously obtained using point-of-care ultrasound by placing the transducer at the right hypochondrium/right lateral region of the corpus. Portal vein flow velocity is obtained by using pulsed

wave Doppler measurements of the left portal vein. In addition, a non-invasive measuring device to assess the mechanical energy of the heart by registering its vibrations (i.e., Kinocardiography, HeartKinetics, Waterloo, Belgium) is put on the participant with sticky-gel electrodes. A 90-second measurement is done once the patient is in the supine position. The same measurement is performed simultaneously by a smartphone application with the smartphone placed centrally on the participant's chest.

To minimize interobserver variability, the same sonographic equipment will be used by the same, independent researcher. Measurements are obtained in supine position at the end of the respiratory cycle (end-expiratory). In order to correlate the study outcome with clinical situations, demographic characteristics of the participants are collected.

6. Safety precautions

There are no known risks except for those of the clinically indicated right heart catheterisation. Echocardiography can cause local discomfort and in rare occasions contusion from local pressure. The Kinocardiography device is completely non-invasive as well, although theoretically, there might be some skin irritation due to its attachment with sticky-gel electrodes.

7. Statistical analysis

a. Main statistical analysis

The correlation between PVPI and RAP, CVP and HVWP will be assessed by classic regression and Bland-Altman plots. A regression formula for RAP will be constructed based on PVPI and age, gender, height and weight if the latter are contributory.

8. References

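### Does the feasibility aim in section 2 need its own endpoint, given that sections 3 and 7 deal only with accuracy?

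*Protocol*

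**What the plan says.** Section 2 (Purpose & rationale) closes with the aim: "The aim of this proof-of-concept study is to assess the feasibility of portal vein Doppler flow to quantify RAP/CVP", to be studied "in a population of consecutive patients with advanced heart failure undergoing invasive right heart catheterization". This is the only place where feasibility is mentioned.

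Section 3 (Objective) contains one objective: "To evaluate the accuracy of the portal vein pulsatility index (PVPI=Vmax-Vmin)/Vmax) to quantify invasively measured right-sided venous pressures".

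Section 4.b (Exclusion criteria) lists, among others, "Major anatomical variations of the portal veins (agenesis of left and right portal vein) and/or arterio-portal vein fistula".

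Section 5 (Intervention) states that "PVPI is simultaneously obtained using point-of-care ultrasound". It has no rule for a recording that fails or cannot be read.

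Section 7.a (Main statistical analysis) gives two analyses. The first is: "The correlation between PVPI and RAP, CVP and HVWP will be assessed by classic regression and Bland-Altman plots". The second is: "A regression formula for RAP will be constructed based on PVPI and age, gender, height and weight if the latter are contributory".

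**The concern.** Feasibility often has a specific meaning in imaging studies: the share of patients in whom the measurement can be made. With that meaning in mind, section 2 announces a question that the rest of the protocol drops. Section 3 replaces it with accuracy, section 5 treats the trace as something that will be there, and section 7 uses only patients who have one.

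Failure of the scan is plausible. One researcher takes pulsed-wave Doppler of the left portal vein at the bedside, at end-expiration, with the patient supine and undergoing catheterisation.

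Three things would be at stake on this reading:

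- The study could end without an endpoint that answers its stated aim.
- The accuracy results would describe patients with a readable trace, while section 2 speaks of consecutive patients.
- The denominator for a feasibility rate would be open, because section 4.b does not say how to count an anatomical variant first seen at the study scan.

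An aim and an objective belong in the protocol, so an unseen statistical analysis plan would not by itself answer a true conflict between them.

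**Working it through.** The protocol states no sample size, failure rate or target for this point, so there is no figure of its own to reproduce. The check is mainly of the text.

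**Step 1. What is feasibility attached to?**

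| Place | What is to be done | To what |
|---|---|---|
| Title | quantify, as a proof of concept | right-sided congestion |
| Section 2 | feasibility to quantify | RAP/CVP |
| Section 3 | accuracy to quantify | invasively measured right-sided venous pressures |
| Section 7.a | regression, Bland-Altman, formula for RAP | RAP, CVP, HVWP |

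In all four rows the task is to relate the Doppler signal to a pressure. Section 2 does not speak of the feasibility of obtaining, recording or reading a trace. In a proof-of-concept study, feasibility to quantify is naturally read as asking whether the index can quantify the pressure at all. Section 3 asks the same in other words, and section 7 addresses it.

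**Step 2. Is obtainability a study question anywhere?** No section names an acquisition rate, a success rate or scan failure as an outcome. The obtainability reading therefore rests on one word taken apart from the phrase it belongs to.

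**Step 3. Could section 7 answer obtainability if it were asked?** No. A patient without a PVPI enters neither analysis. Assume 30 complete pairs. With exact (Clopper-Pearson) 95% intervals, which for 30/30 have lower limit 0.025^(1/30) = 0.884:

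| Enrolled (assumed) | Share with a trace | Exact 95% CI |
|---|---|---|
| 30 | 30/30 = 100% | 88.4% to 100% |
| 33 | 30/33 = 91% | 75.7% to 98.1% |
| 38 | 30/38 = 79% | 62.7% to 90.4% |
| 43 | 30/43 = 70% | 53.9% to 82.8% |

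Regression and Bland-Altman results would be identical in all four rows. But the rows are told apart by two counts, patients enrolled and patients analysed, which any report of participant flow gives.

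**Step 4. Does the wording affect the accuracy estimate?** Assume bivariate normal data with a true r of 0.60.

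- Scans fail at random: r stays at 0.60.
- The highest-RAP patients fail: with v the variance of RAP left after removal (full variance 1), r becomes 0.60√v / √(0.36v + 0.64). For 10% removed, v = 0.712 and r = 0.506/0.947 = 0.535. For 20%, r = 0.497.
- The patients with the largest residuals of RAP on PVPI fail: with w the residual variance left (full residual variance 1), r becomes 0.60 / √(0.36 + 0.64w). For 10% removed, w = 0.623 and r = 0.60/0.871 = 0.689. For 20%, r = 0.750.

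The shift may be nil, downward or upward, and nothing in the protocol favours any of these patterns. This is selection by readable trace, which arises in any study of a measurement that can fail. It would remain exactly as it is if section 2 were reworded.

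**The case for a change.** The strongest case for a change is that the protocol never chooses between the two readings, and that the aim is the protocol's business. An analysis plan that follows section 3 faithfully would carry no feasibility objective. Even on the milder reading there is no criterion for calling quantification feasible. The remedy is cheap, and a log of failed scans has to be kept as the study runs, because reasons not recorded at the time may be lost.

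Part of this stands. The word is used once, undefined, and section 2 would be clearer if it matched section 3. If the sponsor did intend obtainability as an aim, an endpoint would be missing, and section 7 could not fill the gap.

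The rest is weaker. The absence of a pass mark is no fault in a proof-of-concept study whose output is an estimated relation and its agreement. What counts as an analysable trace, how failures are listed and which interval is used are details commonly left to an analysis plan, which may exist. Section 7.a is headed as the main analysis and does not claim to be exhaustive. The section 4.b question has a plain answer on the text: the criterion carries no condition on when the variant is found, so a variant found at the study scan is an exclusion. It becomes a puzzle only once a feasibility rate has been added.

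**Conclusion.** No change to the plan is called for. Sections 2 and 3 differ in wording, not in what the study sets out to learn, because both concern whether PVPI can quantify right-sided venous pressures. Rewording section 2 would change no estimate, interval or conclusion. Adding an acquisition rate would put into the protocol what participant-flow reporting or an analysis plan supplies.

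No size can be given from the protocol. The shares of 70% to 100% and the correlations of 0.50 to 0.75 follow wholly from assumed inputs and show no error in a stated rule.

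The conclusion rests on two assumptions: that feasibility is read together with the words that follow it, and that the report will give the numbers enrolled and analysed, so that readers can see that the accuracy results apply to patients with a readable trace. It would change only if the sponsor meant obtainability as an aim in its own right. The conclusion concerns the match between aim and objective only. Whether the accuracy methods named in section 7 suit their purpose is a separate question.

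### PVPI is acquired simultaneously with the pressures it is compared with, by an 'independent' researcher whom nothing in the protocol masks to those pressures

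*Protocol*

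**What the plan says.** Protocol section 5 describes the invasive reference first: "RAP and CVP assessed at the level of the intrathoracic and intra-abdominal IVC as well as the vena Hepatica is measured". HVWP is measured in the same procedure. The index test runs alongside: "PVPI is simultaneously obtained using point-of-care ultrasound by placing the transducer at the right hypochondrium/right lateral region of the corpus". The trace is a pulsed-wave Doppler recording of the left portal vein.

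Two sentences then standardise the measurements. On the operator: "To minimize interobserver variability, the same sonographic equipment will be used by the same, independent researcher". On the conditions: "Measurements are obtained in supine position at the end of the respiratory cycle (end-expiratory)".

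Section 3 gives the objective: "To evaluate the accuracy of the portal vein pulsatility index (PVPI=Vmax-Vmin)/Vmax) to quantify invasively measured right-sided venous pressures". Section 7 uses the paired readings twice. First, "The correlation between PVPI and RAP, CVP and HVWP will be assessed by classic regression and Bland-Altman plots". Second, "A regression formula for RAP will be constructed based on PVPI", with age, gender, height and weight added if they contribute.

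The protocol has no wording on blinding or masking, concealment of the pressure display, stored or coded recordings, or offline reading.

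**The concern.** An accuracy study can be interpreted only if the index reading is made without knowledge of the reference. Here both are produced in the same session. Obtaining them together is not a fault in itself, since it keeps the haemodynamic state the same for both. It does mean that pressure values may exist in the room while the Doppler trace is being acquired and measured.

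PVPI depends on the operator: someone places the sample volume, accepts a beat and marks Vmax and Vmin. If that person knows the pressure, such choices may be drawn towards it. The association of PVPI with RAP, CVP and HVWP would then look stronger than it is, and the residual scatter of the RAP formula smaller.

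The intended use is also at stake. Section 2 introduces the method against the limits of non-invasive assessment: "Portal vein Doppler flow patterns may be a simple and attractive tool to aid in the evaluation of RAP/CVP". A reading made with the catheter value known is not that use.

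**Working it through.** The protocol gives no figure on this point, so there is nothing to reproduce. The check is a reading of the provisions side by side, followed by a short argument on direction.

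**1. What section 5 fixes, and whether it would conceal the pressures**

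| Provision | What it controls | Conceals the pressures? |
|---|---|---|
| Same equipment | Differences between devices | No |
| Same researcher | Differences between observers | No |
| 'Independent' researcher | Not stated | Depends on meaning (step 2) |
| Supine, end-expiratory | Position and respiratory phase | No |
| Left portal vein, pulsed wave, transducer region | Vessel, mode and window | No |

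The formula for PVPI, in section 3, fixes the calculation but not who marks the velocities or what that person may know.

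**2. What 'independent' could mean**

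- Separate from the catheterisation team: this separates persons, but does not keep a display or a spoken value from someone working at the same time.
- Separate from the sponsor or from the analysis: this has no bearing on what is seen during acquisition.
- Masked to the pressures: this would close the gap, but the protocol does not say it, and the aim given in that sentence is to reduce interobserver variability.

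**3. Which kind of influence would matter**

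Take the simplest case, PVPI against RAP alone, with PVPI = α + β·RAP + e, where e has variance σ², RAP has variance V, and β > 0.

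- A uniform reading habit, PVPI′ = a + b·PVPI with b > 0, leaves the correlation with RAP and the residual scatter of a linear RAP formula unchanged. It does no harm here.
- A habit that follows the known pressure, PVPI′ = PVPI + k·RAP with k > 0, gives r² = (β + k)²V / [(β + k)²V + σ²]. This rises with k, and the residual variance of RAP given PVPI′, V(1 − r²), falls.

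Only the second kind inflates the result, and it requires knowledge of the pressure. The protocol gives no value for β, σ², V or k, and k may be zero. The direction can be stated; the size cannot.

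**4. Whether a later analysis plan could repair it**

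Sample-volume placement is settled at acquisition. Marking of Vmax and Vmin could be repeated without the pressures only if the recordings were kept, and the protocol does not say that they are. Masking therefore belongs with the equipment, operator, position and timing that section 5 already sets.

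**The case against.** The strongest reply is that this is a silence and not a wrong statement. Nothing says that the sonographer sees, hears or is told the pressures. A reader might infer from the word 'simultaneously' that PVPI is read with the pressures in view; the protocol does not support that, and the point does not rest on it.

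Second, 'the same' researcher already serves consistency, so 'independent' presumably adds something, most naturally separation from the catheterisation assessment. That is fair, and it would be wrong to say that every safeguard concerns variability alone. But separation is not masking, and the word is left open.

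Third, fixing the vessel, Doppler mode, transducer region and respiratory phase narrows the operator's freedom. This stands in part: it reduces the scope for influence but does not remove it. How beats and velocities are chosen is not described, so the mechanism rests on general knowledge of Doppler measurement.

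Fourth, a reader might take the dependence of PVPI on where Vmax and Vmin are marked as evidence of bias. It is not: by step 3 of the working, a uniform shift leaves the strength of association unchanged.

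Fifth, this is a single-centre proof-of-concept study with a feasibility aim in section 2. That limits the weight of the point. But section 3 states accuracy as the objective and section 7 builds a prediction formula, and both need an index reading made without the reference.

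**Conclusion.** The point holds in a limited form. The protocol allows PVPI to be acquired and read by someone who knows RAP, CVP or HVWP, because 'independent' is undefined and no other provision conceals the pressures. If that happened and reading choices followed the known values, the accuracy result, the three comparisons in section 7 and the RAP formula would all look better than they should.

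The documents do not show that it will happen, and they do not allow the bias to be sized; it may be zero. The conclusion assumes that PVPI leaves the operator some choice within the fixed vessel, mode and timing. It does not support a claim that the readings will be biased or that the results would be invalid. Section 5 should nevertheless be clarified: the gap touches the only stated objective and an analysis plan could not fully close it.

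**What to change.** In section 5:

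1. State that the researcher who acquires and reads PVPI is masked to RAP, CVP and HVWP, and say that this is what 'independent' means.
2. Keep the pressure display and spoken values from that researcher until Vmax and Vmin are recorded.
3. Log any unmasking, patient by patient.
4. Where practical, store the Doppler recordings, have an existing team member code them, and have the same researcher re-measure Vmax and Vmin without the haemodynamic report. Use this as a sensitivity analysis, or as the main reading for patients in whom bedside masking failed.

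Items 1 to 3 are the main change. Making the coded reading primary for everyone is debatable, because the test is proposed as point-of-care ultrasound and offline reading is not the same as bedside use. Item 4 also has a limit: it cannot undo knowledge that affected sample-volume placement, and the reader is the person who scanned the patient.

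The cost is a minor change to the room set-up, a few protocol sentences, some reading time for the same researcher, and coding by an existing team member. No patient procedure is added.

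### Section 7.a plans Bland-Altman plots of a unitless index against pressures, so their bias and limits cannot measure agreement

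*Protocol*

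**What the plan says.** Section 3 (Objective) defines the index and the aim: "To evaluate the accuracy of the portal vein pulsatility index (PVPI=Vmax-Vmin)/Vmax) to quantify invasively measured right-sided venous pressures". Section 5 (Intervention) takes the velocities from pulsed "wave Doppler measurements of the left portal vein". It also describes the invasive reference measurements: "RAP and CVP assessed at the level of the intrathoracic and intra-abdominal IVC as well as the vena Hepatica is measured", and "In addition, the hepatic venous wedge pressure (HVWP) is measured". The unit of pressure is not stated.

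Section 7.a (Main statistical analysis) has two sentences. The first is "The correlation between PVPI and RAP, CVP and HVWP will be assessed by classic regression and Bland-Altman plots". The second is "A regression formula for RAP will be constructed based on PVPI and age, gender, height and weight if the latter are contributory". Nothing links the Bland-Altman plots of the first sentence to the formula of the second.

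**The concern.** The Bland-Altman method takes the difference between two measurements of the same quantity, in the same unit, and describes that difference by its mean (bias) and its limits (bias ± 1.96 SD). PVPI is a velocity difference divided by a velocity, so it has no unit. A pressure minus a pure number has no physical meaning. The sentence also gives the plot a task it does not perform, since the method describes agreement and not correlation.

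The objective is accuracy in quantifying pressure, and Bland-Altman is the only agreement method the protocol names. If the sentence is followed literally, the report would carry a bias and limits of agreement that a reader could take as the error of a PVPI-based pressure estimate. They are not that error.

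**Working it through.** The protocol gives no mean, SD, correlation or sample size, so there is no figure of its own to reproduce. The mismatch of units needs no numbers; the arithmetic below only shows its effect.

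**Assumed inputs.** RAP mean 10 mmHg, SD 5 (range 3 to 7). PVPI mean 0.40, SD 0.25 as a fraction, equivalent to 40 and 25 as a percentage. Correlation r = 0, 0.6 and 1. The protocol's formula gives a fraction; the percentage is an alternative display of the same data.

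**Formulas.**
- Bias = mean RAP − mean PVPI
- SD of the difference = √(s₁² + s₂² − 2·r·s₁·s₂), with s₁ the SD of RAP and s₂ the SD of PVPI
- Half-width of the limits = 1.96 × SD of the difference
- Regression residual SD = s₁·√(1 − r²)

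**1. Dependence on the display unit, r = 0.6.**
- Fraction: bias 10 − 0.40 = 9.6. SD = √(25 + 0.0625 − 2·0.6·5·0.25) = √23.5625 = 4.85, half-width 9.5.
- Percentage: bias 10 − 40 = −30. SD = √(25 + 625 − 2·0.6·5·25) = √500 = 22.4, half-width 43.8.
- Regression: residual SD = 5·√0.64 = 4.0 mmHg, so ±7.8 mmHg on either scale.

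The pressure unit matters as well. A simulation with PVPI SD 0.20, r = 0.6 and differences taken as PVPI minus RAP gave these results for PVPI as a fraction:

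| RAP unit | Bias | Limits |
|---|---|---|
| mmHg | −9.58 | −19.14 to −0.03 |
| kPa | −0.93 | −2.05 to 0.18 |
| cmH₂O | −13.17 | −26.24 to −0.10 |

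**2. Insensitivity to how good PVPI is, RAP SD 5.**

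| r | Half-width, fraction | Half-width, percentage | Residual SD (mmHg) |
|---|---|---|---|
| 0 | 1.96·√25.0625 = 9.8 | 1.96·√650 = 50.0 | 5.0 |
| 0.6 | 9.5 | 43.8 | 4.0 |
| 1 | 1.96·√22.5625 = 9.3 | 1.96·√400 = 39.2 | 0 |

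On the fraction scale the limits are essentially the spread of RAP. On the percentage scale they are mostly the spread of PVPI. In the simulation, with PVPI as a fraction and RAP in mmHg, the correlation between difference and mean was −1.00 to two decimals at every r tried: the plot shows minus RAP against half of RAP.

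**3. Reversed ranking, fraction scale.**
- Useless index (r = 0), RAP SD 3: 1.96·√(9 + 0.0625) = 5.9.
- Perfect index (r = 1), RAP SD 7: 1.96·(7 − 0.25) = 13.2.

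The useless index has the narrower limits.

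**4. Behaviour of a same-unit comparison.** In the same simulation, predicted against measured RAP in mmHg gave bias 0.00 and limits of ±9.31, ±7.84, ±4.28 and ±0.00 at r = 0.3, 0.6, 0.9 and 1.0. The results were identical for fraction and percentage. These limits do follow accuracy.

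**5. Why the remedy should use cross-validated predictions.** In the fitting sample the mean difference is zero by construction and the limits are too narrow. Assume R² = 0.36, so the residual SD is σ = 4.0, and p = 5 predictors (PVPI and all four covariates).
- In-sample half-width = 1.96·σ·√((n − p − 1)/(n − 1))
- New-patient half-width = 1.96·σ·√((n + 1)(n − 2)/(n(n − p − 2)))

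| Assumed n | In-sample | New patient |
|---|---|---|
| 20 | 6.7 | 9.5 |
| 30 | 7.1 | 8.8 |
| 50 | 7.4 | 8.4 |
| 100 | 7.6 | 8.1 |

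Leave-one-out half-widths in simulation (4000 runs per n) were 9.78, 8.98, 8.46 and 8.13.

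**The case against.** The strongest reply is that the authors meant fitted against measured pressure. Regression is named first and a RAP formula follows, so a plot of predicted against measured values would be a natural sequence. A regression for each of the three pressures could supply fitted values for CVP and HVWP too. This may well be the intent, but the text pairs PVPI itself with the pressures and never mentions predicted values in connection with the plots. If that was the intent, the correction is only a clarification.

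A second reply is that this belongs in a statistical analysis plan. That holds for details such as confidence intervals, reporting of the residual SD and cross-validation, whose absence from a protocol is not an error. It does not hold for the central point: the protocol itself fixes a named method for named variables that the method does not fit, and a plan faithful to it would repeat the error.

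Three narrower points stand:
- The percentage contrast uses a scale the protocol does not mention. The stronger evidence is on its own fraction scale (±9.8 against ±9.3).
- The in-sample comparison concerns optimism and not units. It supports the form of the remedy, and it assumes all four covariates are kept, whereas section 7.a keeps them only if they contribute.
- Section 5 has venous pressure measured at more than one site, so the number of extra regressions may exceed two.

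**Conclusion.** The concern holds. Followed as written, section 7.a yields a bias and limits that carry no agreement information. With the assumed means and SDs, the limits move only from ±9.8 to ±9.3 between a useless and a perfect index, and they can rank a useless index above a perfect one. Those sizes rest on assumed values, but the mismatch between method and variables does not.

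The consequence is bounded. The regression and the RAP formula are valid, and their residual SD can express error in pressure units. No data are lost and no decision rule uses the limits. The sentence should be fixed before analysis; it does not threaten the study.

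**What to change.** Rewrite the first sentence of section 7.a so that:

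- For raw PVPI against each pressure, the analysis reports the correlation and the regression slope with 95% confidence intervals, and the residual SD in pressure units.
- Bland-Altman is applied only to pressure predicted from the PVPI regression against the measured pressure, in the same stated unit. This covers RAP and, with a regression for each, CVP and HVWP. The sentence should name the CVP site or sites.
- The mean difference and 95% limits of agreement are given with confidence intervals and computed from cross-validated predictions.

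The cost is an amended sentence, at least two further regressions (more if CVP is analysed at several sites) and the cross-validation. No new data are needed. The signature page commits the investigator "not to implement any deviations from or changes to the protocol without prior review and written approval from the Ethics Committee", so the change should go through as an amendment.
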